(CI), which results in the improvement of systemic and end-organ perfusion, as well as the reversal of cardiogenic shock. Impella RP placement has also been shown to decrease central venous pressure (CVP) (Anderson). This improvement in hemodynamics facilitates the weaning of inotrope and vasopressor support. LVAD flow has also been shown to improve after Impella RP support is initiated (Anderson).

ProtekDuo, manufactured by TandemLife, is another device placed percutaneously for right heart support via the right internal jugular (RIJ) vein. Like the Impella RP, use of the ProtekDuo is associated with improved hemodynamics in patients with right ventricular failure. Studies looking at concomitant insertion of the ProtekDuo and LVAD to preempt RVF in patients with impaired RV function have shown advantageous effects on patient outcomes compared to insertion post-LVAD (Schmack). It is expected that preemptive placement of RVADs prior to or during LVAD implantation to preemptively treat RVF will similarly result in improved patient outcomes.

III. SPECIFIC AIMS

The purpose of this study is to compare clinical outcomes of standard of care treatment versus preemptive percutaneous right ventricular assist device (RVAD) placement surrounding left ventricular assist device (LVAD) implantation. We hypothesize that the use of the RVAD will mitigate need for inotropic support, reducing the vasoactive-inotrope score (VIS) by 50%, and will improve end organ function in patients compared to standard of care.

IV. SUBJECT SELECTION

This trial will include both a prospective interventional cohort and a retrospective control cohort. The prospective interventional cohort will consist of patients undergoing LVAD implantation at Massachusetts General Hospital. These patients will receive an RVAD (either the ProtekDuo or Impella RP) prior to or during LVAD implantation. The historical control cohort will consist of retrospective data collection on patients who have undergone LVAD implantation in the past. This group will be age and sex matched with the enrolled prospective interventional patients.

INCLUSION:

- Ages 18-75
- Accepted for LVAD implantation by MGH multidisciplinary team

EXCLUSION:

- Disorders of the pulmonary artery wall that would preclude placement or correct positioning of RVAD
- Presence of mechanical valves
- Mural thrombosis of the right atrium or vena cava
- Anatomic conditions precluding insertion of the RVAD

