- Complicated venous access precluding or complicating device placement (i.e. femoral and jugular thrombosis)
- No evidence of right ventricular dysfunction by echocardiogram

V. SUBJECT ENROLLMENT

Potential study subjects will be identified only after they have been deemed eligible and appropriate for LVAD implantation.

The primary specialist/healthcare provider who is known to the potential subject and has firsthand knowledge of the patient's medical history will give approval for his/her patient to be contacted for research purposes. The primary specialist/healthcare provider will introduce the study and obtain the patient's/family's permission to be contacted by study staff verbally. Potential participants may be identified from among the PI's, or Co-Investigators' direct patient populations. It will be made clear to the subject that participation in the study is entirely voluntary and that their decision will not affect their care now or in the future.

The Investigator will explain the research study to the potential subject in detail including the purpose of the research, procedures, risks and potential benefits, right to withdraw, alternative care and confidentiality. Subjects will be given a copy of the consent form to review to ensure the subject is able to understand the study. Potential subjects will be encouraged to speak with friends/family and/or other healthcare providers about research participation. Subjects are told that the PI will also be available to discuss the study.

Once a subject decides to participate, a licensed physician investigator will obtain informed consent from the subject. The consent discussion between the investigator and patient participant will be documented in the research record. Subjects will be given a copy of their signed consent form. The original signed consent form will be retained in the study binder. A copy of the signed consent form will be filed in the subject's medical record. Should the participant have additional questions, a licensed physician investigator will be offered (and made available) to discuss the consent questions.

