A physician Investigator will approach the surrogate using the same process as outlined in obtaining consent for all subjects. The study will be explained in full to the surrogate, including the purpose of the research, procedures, risks and benefits, right to withdraw, alternative care and confidentiality. We will ensure and document that the surrogate understands that his/her decisions should be based on substituted judgment. If a potential subject did not previously express a view, the surrogate should make the decision based on the potential subject's best interests. We will explain the difference between standard of care and research.

If surrogate consent is obtained, the basis of the determination of the subject's lack of capacity will be documented in the research records, along with a description of the relationship of the surrogate.

After consent is signed, subjects in the prospective interventional cohort will be assigned to receive either the Impella RP or ProtekDuo, as indicated by the treating physician. The RVAD will be placed within 48 hours preoperatively of the LVAD implantation, at the time of LVAD implant, or immediately following the implant. The RVAD will be left for up to 72 hours. RVAD management will be performed according to MGH standard of care by the medical staff.

There will be no consent process for the historical control cohort as there are no interventions for this group. The clinical data required for this study is already collected in a secure database per standard of care.

VI. STUDY PROCEDURES

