All LVAD candidates at Massachusetts General Hospital (MGH) will be screened for trial eligibility. Every eligible candidate will be asked to participate. Subjects who consent to the study will undergo pre-operative or intra-operative placement of an RVAD, which will be left in up to 72 hours postoperatively. If it is determined that a subject requires support for longer than 72 hours, the treating physician will consider utilizing a more durable form of right ventricular support (CentriMag paracorporeal RVAD requiring direct cannulation), as is standard practice. The type of RVAD (Impella RP or ProtekDuo) inserted will be determined by patient needs and venous access and will be up to the discretion of the treating physician. The use of the ProtekDuo will be prioritized due to the benefit of the jugular approach in device placement, which does not limit patient mobility. If there is no jugular access, the Impella RP, which is placed through a femoral approach, will be used. We aim to enroll 25 subjects in the prospective interventional cohort, and compare to 25 subjects in the matched retrospective control cohort.

All enrolled patients in the prospective interventional cohort will undergo surgical placement of a percutaneous RVAD within 48 hours preoperatively to LVAD implantation, at the time of LVAD implant, or immediately following the implant. After removal of the RVAD, subjects will receive standard treatment according to MGH's standard of care. Data will be obtained for subjects in both cohorts from the electronic medical record in EPIC at MGH and will be reviewed throughout the study through the 1-year follow-up period. Other standard of care tests are administered regularly at LVAD follow-up visits, including: the KCCQ-12 and EQ-5D surveys, a neurocognitive trailmaking test, and a six-minute walk and gait speed test. These are collected per standard of care at the following timepoints: pre-implant, 3 month (+/- 30 days), 6 month (+/- 60 days), and 1 year (+/- 60 days). These results will also be collected and entered to the study database.

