Clinical data will be collected and entered into the secure database by study coordinators. All subjects will be followed through 12-month post-LVAD implantation with data collection occurring at the following timepoints: pre-implant, time of implant, discharge, 1 week (+/- 3 days), 1 month (+/- 7 days), 3 month (+/- 30 days), 6 month (+/- 60 days), and 1 year (+/- 60 days), all of which will align with routine clinical standard of care visits. Subjects will not be asked to come for additional visits separate from their usual standard of care visits. All follow-up tests and procedures will also be done per standard of care.

VII. DATA COLLECTION SCHEDULE

DATA COLLECTION SCHEDULE									
ASSESSMENT	Pre-LVAD Implant	RVAD Placement	LVAD Implant	1 Week Follow-up	Implant Discharge	1 Month Follow-up	3 Month Follow-up	6 Month Follow-up	1 Year Follow-up
Screening	X								
Demographics	X								
Medical History	X								
RVAD Placement Details		X	X						
LVAD Implant Details			X						
Discharge Details					X				
Status	X			X		X	X	X	X
Right Heart Failure Assessment				X		X	X	X	X
Hemodynamics	X			X		X	X	X	X
Medications	X			X	X	X	X	X	X
Laboratory	X			X		X	X	X	X
Device Details							X	X	X
Exercise/Trailmaking	X						X	X	X
Quality of Life	X						X	X	X
Adverse Events		X	X	X		X	X	X	X

VIII. BIostatistical Analysis

STUDY VARIABLES

Eligibility Data

Potential study participants who have left-heart failure and are planned to undergo LVAD placement will be approached by the study staff. The study will be explained, and these potential participants will be provided with study information and consent forms. Potential participants who meet study criteria will be assigned a unique identifier at this time (regardless if they are enrolled, which will ensure accurate recording of number of screened vs. enrolled patients). Enrolled subjects in the prospective arm will be matched to historical controls, which will consist of patients who underwent LVAD implantation in the past in the absence of pre-operative or concurrent percutaneous RVAD placement.

Demographics – collected at outpatient visit when patient is being considered for LVAD placement
Demographic data assessed and recorded at the initial screening visit will include date of birth, gender, race, and ethnicity.

Comorbidities

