Past medical history will be assessed at the time of screening and documented at the time of enrollment. Data collected will relate to underlying cardiovascular pathology and to associated pathology of the pulmonary, renal, hepatic, endocrine, hematologic, or neurologic systems.

Medications

Data on both active and past medications will be collected at the time of initial screening. If the patient is admitted at the time of screening, both current inpatient medications and home medications will be recorded. If the patient is outpatient at the time of screening, home medications will be recorded. Record of active medications will also be collected at each timepoint throughout the study.

Laboratory Data

Pre- and post-operative lab data including but not limited to CBC, CMP, INR, NT-pro-BNP will be collected at various timepoints during the study, including at time of enrollment.

EKG, ECHO, and Cardiac Catheterization assessment

EKG, ECHO, and Cardiac Catheterization results will be collected at several points during the study.

Inpatient Events/Procedures

Data on events and procedures that occur while patients are admitted will be collected on an ongoing basis while study participants are admitted to the hospital. Where complications occur, adverse event forms will be completed and principal investigators will be notified.

PRIMARY ENDPOINT

The primary outcome of the study will be the vasoactive inotropic score (VIS). Both the average/mean VIS and the cumulative VIS over the first 24 hours post-LVAD implantation of the experimental cohort (those enrolled in the prospective study who undergo pre-emptive RVAD placement) will be compared to a historical cohort of patients who received the current standard of care. The VIS will be calculated for each patient in both arms of the study. Both the maximum score and the cumulative sum achieved in the first 24 hours after LVAD implantation will be recorded (maximal 24-hour VIS and cumulative 24-hour VIS).

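### Historical controls have no implant-date window and no stated rule for choosing among age/sex matches, so drift in vasoactive drug practice is uncontrolled and outcome-blind selection is not assured

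*Protocol*

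**What the plan says.** The control cohort is defined in two places in the Protocol.

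- IV. Subject Selection: "The historical control cohort will consist of retrospective data collection on patients who have undergone LVAD implantation in the past". On matching: "This group will be age and sex matched with the enrolled prospective interventional patients".
- VIII. Biostatistical Analysis, Eligibility Data: the controls are patients "which will consist of patients who underwent LVAD implantation in the past in the absence of pre-operative or concurrent percutaneous RVAD placement".

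Four other passages bear on who the controls can be:

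- V. Subject Enrollment, explaining why controls need no consent: "The clinical data required for this study is already collected in a secure database per standard of care".
- VI. Study Procedures: "Data will be obtained for subjects in both cohorts from the electronic medical record in EPIC at MGH". The same section invites every eligible candidate to join and gives the RVAD to those who consent, so there is no concurrent control arm. It plans 25 treated patients and 25 controls.
- VIII, Primary Endpoint: the controls are described as having received current standard care, with no dates. On the score itself: "The VIS will be calculated for each patient in both arms of the study". The primary test is a two-sided t-test at 0.05, with no adjustment named.
- IV, exclusion list: "No evidence of right ventricular dysfunction by echocardiogram" is an exclusion. The Protocol does not say whether the list applies to controls.

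Nowhere is there an implant-date window, a consecutive-patient rule, or an order for choosing among several patients of suitable age and sex.

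**The concern.** VIS is built from the doses of six vasoactive drugs (II. Background and Significance), and clinicians set those doses. The score can therefore move with unit practice while right ventricular function stays the same. Because treatment and calendar period coincide completely, a change in practice between the control years and the enrolment years enters the treatment comparison in full. Matching on age and sex does nothing about it.

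The second exposure is the choice of controls. They are matched to patients already enrolled, from records that already contain the drug data. If two or more past patients fit a case, the Protocol does not say which is taken, or that the person choosing cannot see post-implant drug use.

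What is at stake is the reading of the primary result: a significant difference could reflect period or selection, and a real difference could be obscured. Enrolling more patients would not help, because bias does not shrink with sample size.

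**Working it through.** **The plan's own figure.** VIII, Power Analysis gives 17 per group for 80% power, two-sided 0.05, SD 0.5. With a difference of 0.5 and SD 0.5, the standardised effect is 1.
- Normal approximation: n = 2 × (1.960 + 0.842)² / 1² = 15.7, so 16 per group.
- Exact t-test: 16.7, so 17 per group, with power 0.807. The figure is reproduced.

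The scale of the SD is not stated. I therefore use log-scale SDs of 0.5 and 0.69. The second, ln 2, is the SD that makes a halving of VIS equal to a standardised effect of 1.

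**Effect of drift alone.** Inputs: n = 25 per group, two-sided 0.05 and no RVAD effect. The drift is assumed, since the Protocol gives none.
- Standardised shift: d = −ln(1 − drift) / SD.
- Noncentrality: d × √(25/2) = 3.536 d, with 48 degrees of freedom and critical value 2.011.

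| Assumed fall in VIS | d, SD 0.5 | Significant for RVAD | d, SD 0.69 | Significant for RVAD |
|---|---|---|---|---|
| 10% | 0.211 | 10.9% | 0.152 | 7.6% |
| 20% | 0.446 | 34.0% | 0.322 | 19.9% |
| 30% | 0.713 | 69.5% | 0.515 | 43.0% |

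The nominal rate in that direction is 2.5%. On an additive scale with SD equal to half the control mean, d is 0.2, 0.4 and 0.6, and the rates are 10.3%, 28.3% and 54.7%. Sample size makes it worse: at a 20% fall and log-SD 0.5, the rate is 24.3% with 17 per group and 34.0% with 25.

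**Drift the other way.** Suppose practice raised VIS by 20% between the periods.
- A true 25% reduction would appear as 0.75 × 1.20 = 0.90, a 10% fall. At log-SD 0.5, the chance of a significant result drops from 51.3% to 10.9%.
- The hypothesised 50% reduction would appear as 0.50 × 1.20 = 0.60, a 40% fall. Power goes from 99.8% to 94.3% at log-SD 0.5, and from 93.4% to 72.3% at 0.69.

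Masking therefore matters most if the true effect is smaller than planned.

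**Selection alone, as an illustration.** Assume no drift, no device effect and two candidates per case, with the higher-VIS candidate taken in a share q of cases and a random one otherwise. The mean shift is q × 0.56 SD. In 40,000 simulated trials the favourable false-positive rate was 3.9% at q = 10%, 7.0% at 25% and 16.8% at 50%. With a 20% fall at log-SD 0.5 and q = 25% together, it was 53.6%. These shares are assumptions; nothing in the Protocol suggests any of them.

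**The case against.** The sponsor can fairly say that the pool is not open-ended. It is limited to one hospital's electronic record and to patients without a percutaneous RVAD before or during implantation. The Primary Endpoint section also describes the controls as having received current standard care. That is a restriction of sorts on era. It stands, but it is tied to no dates and so cannot be applied as a rule.

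The sponsor can add that matching algorithms and list locks often sit in an analysis plan, which may exist and is not at hand. That is true of tie-breaking detail. Who the controls are is a design decision, though, and the Protocol has made it: past implants, age and sex. A later plan could add covariates but could not separate period from treatment where the two do not overlap.

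A reader might infer more than the text supports:

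- **That controls will be picked with their VIS in view.** The Protocol says VIS is calculated for the study. What is on file is the underlying drug data, and nobody is said to look at it when choosing. Outcome-aware selection is not ruled out; it is not planned.
- **That implants of any age will be used, or that older pump models will distort VIS.** No passage describes the age of the pool, a change of LVAD model, or a link from model to VIS.
- **That the bias must favour the device.** Drift can run either way. If the right ventricular exclusion is not applied to controls, they could have healthier right ventricles, which would work against the RVAD.

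**Conclusion.** The concern holds in this limited form. The stated rule leaves the calendar period of the controls open and does not fix how they are chosen, for an endpoint that clinicians titrate, in a comparison where period and treatment do not overlap. It is not an objection to historical controls as such, and it disputes no stated sample size.

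The size depends on assumed drift. Over falls of 10% to 30%, the chance of a false significant result favouring RVAD runs from about 8% to 70% across the two log-scale SDs, against 2.5%. A rise in VIS over time would instead hide part of a true effect. The documents give no evidence on the amount or direction of drift, so these figures show how sensitive the design is; they do not forecast an error rate. The point is a worthwhile improvement because the exposure could decide the primary result and is cheap to limit.

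**What to change.** In IV. Subject Selection and in the Eligibility Data paragraph of VIII:

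1. Define the control pool as consecutive LVAD implants at the hospital that meet the same eligibility criteria and had no percutaneous RVAD before or with the implant. Count back from the date of first enrolment, only as far as the matches require.
2. Match on nearest implant date as well as age and sex.
3. Choose controls by a written algorithm from a file without post-implant drug or outcome data, and lock each batch before VIS is calculated. If the interim analysis after the first 10 subjects (XI. Monitoring and Quality Assurance) uses controls, matching has to be done in stages, with a lock at each.
4. Report implant year by cohort, and state that residual period confounding remains. Nearest-date matching narrows the gap between periods but cannot close it.

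The cost is a short Protocol amendment and an ordered data pull from the existing record, with no new patients. The downside is a smaller pool and looser age matches, plus some extra handling if matching is staged.

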The primary analysis will be performed in an intention-to-treat fashion using a two-sided T-test (alpha level=0.05). The null hypothesis is that the mean maximal 24-hour VIS will not differ between intervention and historical groups. The alternate hypothesis is that compared to standard of care (historical cohort), placement of an RVAD within 48 hours before or during LVAD implantation will decrease the mean maximal 24-hour VIS score by 50%. Analysis assumptions will include independence of study groups and lognormal (or normal) distribution of data in each group.

SECONDARY OUTCOMES

Secondary end points will include:

- Total VIS (throughout hospitalization)
- ICU length of stay (LOS)
- Total post-operative LOS after LVAD implantation
- Survival at discharge after LVAD placement
- Survival at 1 year after LVAD placement or heart transplant
- End organ dysfunction including
 - o Development of acute kidney injury (AKI) – defined as increase in serum creatinine (sCr) to 4mg/dl or greater, a 150% or greater increase in sCr over the baseline preoperative value, or a new requirement for renal replacement therapy
 - o Liver dysfunction
- LVAD device speed

Cox proportional hazard models (one sided, 0.05 significance level) will be used to compare rates of secondary outcomes between intervention and historical arms. Event rates and relative risks will also be estimated for each of these outcomes.

POWER ANALYSIS

Sample size calculations are estimated based on expected effect size, which was determined based on expert consensus (reduction in the mean maximal 24-hour VIS score by 50% in the intervention arm compared to the historical controls). 80% power will be generated with 2-tailed confidence interval of 0.05 from a sample size of 34 patients (17 per group). Estimating a

standard deviation of 0.5 of the outcome in the population and 20% attrition and/or cross-over, investigators anticipate that 20 patients will be needed to test this hypothesis. This power estimation assumes a lognormal distribution of the data. We plan to allow for 25 patients to participate in the prospective arm of the study to allow for incorrect assumptions.

IX. RISKS AND DISCOMFORTS

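### Primary Endpoint compares mean and cumulative 24-hour VIS, but the hypotheses and sample size concern maximal 24-hour VIS only, and cumulative VIS has no rank

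*Protocol*

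**What the plan says.** All of this is in section VIII of the protocol. The Primary Endpoint text names the outcome only as VIS, without choosing a summary. It then says that "Both the average/mean VIS and the cumulative VIS over the first 24 hours post-LVAD implantation of the experimental cohort" will be compared with a historical cohort given standard care. Shortly afterwards the pair changes: "Both the maximum score and the cumulative sum achieved in the first 24 hours after LVAD implantation will be recorded".

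The next paragraph gives one primary analysis, a two-sided t-test at 0.05, in a sentence that names no variable. The hypotheses follow at once and are specific: "The null hypothesis is that the mean maximal 24-hour VIS will not differ between intervention and historical groups". The alternative is a 50% fall in the same quantity. The Power Analysis rests on the same variable, a "reduction in the mean maximal 24-hour VIS score by 50% in the intervention arm compared to the historical controls".

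In Secondary Outcomes the only VIS item is total VIS over the hospital stay; cumulative 24-hour VIS is not listed. For the secondary outcomes the rule is: "Cox proportional hazard models (one sided, 0.05 significance level) will be used to compare rates of secondary outcomes".

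**The concern.** Three summaries of one 24-hour record are in play: mean, maximum and cumulative sum. Read literally, the sentence on what is compared leaves out the maximum, which is the only summary with a hypothesis and a sample size. The mean may be meant as the group mean of each patient's maximum. That reading removes one mismatch, but cumulative 24-hour VIS remains under the primary heading with no hypothesis and no rank.

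What is at stake is the claim the trial may make. The controls are historical, their data already exist, and the protocol provides for no blinding. If maximal VIS showed no difference and cumulative VIS favoured the device, the Primary Endpoint text would give cover for reporting the latter as a primary result. The two need not agree: faster weaning after an unchanged early peak would lower the sum and leave the maximum alone.

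**Working it through.** **1. The plan's own sample size, and which variable it serves.** Inputs from Power Analysis: 50% reduction in mean maximal 24-hour VIS, SD 0.5 (scale not stated), two-sided 0.05, 80% power, 17 per group. Taking the reduction as 0.5 on the same scale as the SD gives a standardized effect d = 0.5/0.5 = 1.0. This is inferred; the protocol does not state it.

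- Normal approximation: n = 2 × (1.960 + 0.842)² / d² = 2 × 7.85 / 1 = 15.7, so 16 per group.
- t-test (noncentral t): 16.7, so 17 per group. Power is 78.1% at 16 and 80.7% at 17.

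The stated 17 reproduces. If the SD of 0.5 were on the log scale, d would be ln 2 / 0.5 = 1.39 and the t-test would need 10 per group. On either reading the inputs belong to maximal VIS. The protocol gives no effect size or SD for cumulative or mean VIS.

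**2. The summaries side by side.**

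| 24-hour VIS summary | Named as compared | Named as recorded | In the hypotheses | In Power Analysis | In the secondary list |
|---|---|---|---|---|---|
| Mean | yes, read literally | no | no | no | no |
| Maximal | no | yes | yes | yes | no |
| Cumulative | yes | yes | no | no | no |

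**3. Two readings of the t-test sentence.**

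- *It covers maximal VIS only.* The confirmatory test is then clear, and the other summaries are compared under the primary heading with no stated status.
- *It covers every VIS comparison in the section.* Cumulative VIS then has a test and a level, but a single 0.05 is used two or more times with no adjustment or order.

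**4. Size on the second reading, if success on either measure were enough.** The planned size is 25 against 25 (section VI, Study Procedures). The chance of at least one false positive from two tests at 0.05 is 1 − 0.95² = 0.0975 if they are independent. The documents give no correlation between the measures, so a range is assumed. The results come from 400,000 simulated null trials per value, with bivariate normal data and two-sided t-tests (Monte Carlo standard error at most 0.0005):

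| Assumed correlation | Family-wise error |
|---|---|
| 0.6 | 0.088 |
| 0.7 | 0.084 |
| 0.8 | 0.079 |
| 0.9 | 0.071 |
| 0.95 | 0.065 |

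Two summaries of the same 24 hours probably lie toward the lower error figures.

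**5. Whether the mean adds a third test.** On a complete, fixed grid of K readings, mean = cumulative / K. Dividing every value by K leaves the t statistic unchanged. On the log scale it shifts both groups by ln K, which also leaves it unchanged. Mean and cumulative VIS would then be one test, so the mean adds little.

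**6. What would happen on a simple move to the secondary list.** The stated secondary rule is one-sided at 0.05 (critical value 1.645 against 1.960 for two-sided 0.05) and uses a Cox model. It would be more lenient than the primary test, and a Cox model does not suit a continuous score. Total VIS, already in that list, has the same difficulty.

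**The case against.** The strongest reply is that the confirmatory claim is already settled. There is one null, one alternative and one sample size, and each names mean maximal 24-hour VIS. On that view cumulative VIS is a supportive measure under the wrong heading, and selective reporting is a forecast, not an error in the planned test. Much of this stands: the hypotheses do point to maximal VIS, and neither the primary test nor the sample size needs to change. It does not explain why the comparison sentence names other summaries, or what standing a favourable cumulative result would have.

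It can also be said that ranking supportive measures belongs in a statistical analysis plan, which is not shown here. That would hold for an omission. Here the protocol places a comparison under its Primary Endpoint heading that its own hypotheses do not cover, so the inconsistency is in this document.

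A third reply is that the Cox rule speaks of rates, so it may never have been meant for continuous scores. That is possible, but the protocol gives no other rule for them.

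A reader might go further and infer that the trial runs at a false-positive rate of 6.5% to 8.8%, or that cumulative VIS is a co-primary endpoint. The documents support neither. Nothing says that success on cumulative VIS would suffice, and the correlations are assumed. Nor can it be stated as fact that cumulative VIS has no alpha, because the t-test sentence names no variable.

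**Conclusion.** The point holds as an inconsistency inside the protocol about what the primary endpoint is. The comparison sentence does not clearly name the measure that is hypothesised and powered, and cumulative 24-hour VIS has neither a hypothesis nor a place in the secondary list. This is firm on the text, and for cumulative VIS it does not depend on how the word mean is read.

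The consequence depends on the t-test sentence: unranked summaries open to selective emphasis, or unadjusted use of one 0.05. The family-wise figures illustrate only the second case, under an either-suffices rule that the protocol does not contain. The planned test of maximal VIS and its sample size are not affected. The correction should be made because it costs little and settles in advance what may be claimed.

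**What to change.** - In Primary Endpoint, state that maximal 24-hour VIS is the single primary endpoint, tested at two-sided 0.05 as the hypotheses already imply, and make the comparison and recording sentences agree with that.
- Add cumulative 24-hour VIS to Secondary Outcomes. Mean 24-hour VIS can be dropped, for the reason in step 5; if it is kept, list it as secondary too.
- In Secondary Outcomes, state that continuous VIS scores, including total VIS over the hospital stay, are compared by a two-sided test on the same scale (log or original) as the primary, and not by the one-sided Cox rule.

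The cost is a few sentences in section VIII, with no change in sample size. The downside is that cumulative VIS can no longer carry the primary claim.
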